6.2.2 Dose Reductions and Treatment Alterations for Cetuximab

6.2.2.1 Skin Reactions

Prophylactic use of oral tetracyclines is highly recommended for subjects in Arm A for reducing the incidence of Grade 3 skin reactions (34). Unless there are contraindications based on subject and/or health care provider factors, prophylactic systemic treatment with minocycline 100 mg daily or doxycycline 100 mg twice daily is recommended for 6-8 weeks for subjects randomized to Arm A, starting 1 day before the administration of the first dose of cetuximab (34, 35). The recommended prophylaxis for skin toxicities are described in Table 6.2.

Table 6.2 Recommended Prophylaxis for Skin Toxicities

Treatment	Dose	Start	Stop	Alternatives
	Systemic	therapy ¹		
Minocycline	1 × 100 mg/day	Day -1	6-8 weeks ²	In case of intolerance:
Or				• First generation
Doxycycline	$2 \times 100 \text{ mg/day}$			cephalosporins
				 Amoxicillin
				 Erythromycin
				 Limecycline
	Topical t	therapy		
Low potency steroid creams such as:	2 × daily on face and chest	Day -1	6-8 weeks	
• Alclometasone 0.05%				
• Desonide 0.05%				
• Fluocinolone 0.01%				
Emollient (creams or ointments)	3 × daily to the hands, and after hand washing	Day -1	Continue	
	$2 \times \text{daily on}$ the rest of the body			

¹ If infection is suspected (yellow crusts, purulent discharge, painful skin / nares), obtain culture and change to oral antibiotic based on sensitivities.

For a Grade 1 or 2 acne-like rash (as defined in the CTCAE version 4.03), treatment with topical antibiotics (e.g., benzoylperoxide, erythromycin) or systemic antibiotics (e.g., oral tetracyclines) should be considered. Subjects with at least Grade 3 reactions should be referred to a dermatologist for advice and management if needed. If pruritus occurs, an oral antihistamine is advised. In the case of dry skin, the use of emollient creams is beneficial. Fissures may occur in dry skin and topical dressings are helpful.

[figure not shown]
² May be continued beyond 6-8 weeks at the Investigator's discretion in the event of CTCAE Grade 2 rash.

If a subject experiences a Grade 3 skin reaction (as defined in the CTCAE version 4.03), cetuximab treatment may be delayed for up to 14 days (omission of 1 or 2 scheduled administrations) without changing the dose level (see Figure 6.1). If skin reactions resolve to Grade 2 or less by the following treatment period, treatment may be resumed.

If Grade 3 skin reactions occur for a second and third time, cetuximab treatment may again be delayed for up to 14 days with dose reductions to 200 mg/m² and then 150 mg/m². Cetuximab dose reductions are permanent. Subjects must discontinue cetuximab if more than 2 consecutive infusions are withheld or Grade 3 skin reactions occur for a fourth time despite the appropriate dose reduction (see Figure 6.1). Any Grade 4 toxicity (including skin reactions) considered related to cetuximab is to result in discontinuation of cetuximab treatment permanently.

If, in the opinion of the Investigator, the discontinuation of cetuximab is considered necessary, the subject should be withdrawn from cetuximab treatment immediately, but should be further treated with chemotherapy and remain in the trial for scheduled visits.

Treatment Adjustment in the Event of Grade 3 Skin Reactions Figure 6.1 Considered to be Related to Cetuximab

Document No. CCI Object No.

6.2.2.2 Infusion-related Reactions

Mild or moderate infusion-related reactions are very common. Symptoms include fever, chills, dizziness or dyspnea occurring in a close temporal relationship mainly to the first cetuximab infusion.

Severe infusion-related reactions may occur, in some cases with a fatal outcome. Some of these reactions may be anaphylactoid/anaphylactic in nature or represent a cytokine release syndrome. This syndrome typically occurs within 1 hour after infusion and is less commonly associated with bronchospasm and urticaria, but may also occur for up to several hours after infusion or with subsequent infusions. Cytokine release syndrome is normally most severe in relation to the first infusion.

Symptoms of severe infusion-related reaction may include bronchospasm, urticaria, hypertension or hypotension, loss of consciousness, or shock. In rare cases angina pectoris, myocardial infarction, or cardiac arrest have been observed.

Anaphylactic reactions may occur as early as within a few minutes of the first infusion, e.g., due to preformed Immunoglobulin E antibodies cross-reacting with cetuximab. These reactions are commonly associated with bronchospasm and urticaria. They can occur despite the use of premedication.

These symptoms usually occur during the first infusion and up to 1 hour after the end of infusion, but may happen several hours after or with subsequent infusions. It is recommended to warn subjects of the possibility of such a late onset and to instruct them to contact their physician if symptoms of an infusion-related reaction occur. Special attention is recommended for subjects with reduced performance status and pre-existing cardiopulmonary disease.

The Investigator must treat all symptoms of infusion-related reactions with the best available medical measures. Based on previous experience with cetuximab infusion-related reactions, the treatment guidelines given in Table 6.3, graded according to the CTCAE version 4.03 should be followed:

Table 6.3 Treatment Adjustment for Symptoms of Cetuximab Infusion-related Reactions

CTCAE Grade ¹	Treatment adjustment for cetuximab
Grade 1 mild Transient flushing or rash; drug fever < 38°C;	Decrease the cetuximab infusion rate by 50% and monitor closely for any worsening.
Transient flushing of fash, drug fever < 50 C,	The total infusion time for cetuximab should not exceed 240 minutes.
Grade 2 moderate Rash: flushing; urticaria; dyspnea; drug fever ≥38°C	Stop cetuximab infusion and immediately administer treatment for symptoms.
	Resume infusion at 50% of previous rate once infusion-related reaction has resolved or decreased to at least Grade 1 in severity, and monitor closely for any worsening.
Grade 3 or Grade 4 severe or life-threatening Grade 3: Symptomatic bronchospasm, with or without urticaria; parenteral medication(s)	Stop the cetuximab infusion immediately and disconnect infusion tubing from the subject.
indicated; allergy-related edema/angioedema; hypotension Grade 4 Anaphylaxis;	Treat symptoms vigorously. Subjects have to be withdrawn immediately from treatment and must not receive any further cetuximab treatment.

¹ Graded according to Common Terminology Criteria for Adverse Events, version 4.03.

Resumption of cetuximab treatment following infusion-related reactions

Once the cetuximab infusion rate has been decreased after an infusion-related reaction, it must remain decreased for all subsequent infusions. If the subject has a second infusion-related reaction on the slower infusion rate, the infusion should be stopped and the subject should be withdrawn from cetuximab treatment permanently. If a subject experiences a Grade 3 or 4 infusion-related reaction (excluding fever) at any time, she/he must discontinue cetuximab immediately, but should be further treated with chemotherapy and remain in the trial for scheduled visits.

6.2.2.3 Other Reasons

If a subject develops an intercurrent illness (e.g., infection) that, in the opinion of the Investigator and/or Sponsor, mandates interruption of treatment, this intercurrent illness must resolve within a time frame such that no more than 2 consecutive cetuximab infusions are withheld. In the event of delayed cetuximab treatment, there will be no new 400 mg/m² initial dose at treatment restart, and all subsequent treatments will be continued at the assigned dose level or the last dose before interruption if the dose had been reduced.

If cetuximab must be withheld for a longer period of time, cetuximab treatment will be permanently discontinued; in special cases, the Investigator may request that the subject is allowed to continue to receive cetuximab after consulting the Sponsor.

Cetuximab treatment will not be delayed for a chemotherapy-related toxicity. Therefore, if there is a delay for chemotherapy, the subject will continue to receive weekly infusions of cetuximab. If chemotherapy is completely terminated for a related toxicity, cetuximab may be continued as monotherapy up to until either PD, as assessed by the Investigator, unacceptable toxicity, or withdrawal of consent. No other antitumor treatment should be given to subjects until radiographically documented PD. Subjects will continue to receive scheduled evaluation visits until PD, as assessed by the Investigator.

6.3 Assignment to Treatment Arms

All subjects will be assigned a subject number by the Investigator at the screening visit. Subjects who enter the trial will retain this number throughout the trial.

Randomization will occur on Day 1, the same day the trial treatment is initiated, but before the first dose of trial treatment. For subjects randomized to Arm A, prophylactic administration of a tetracycline is recommended, starting 1 day before the administration of the first dose of cetuximab. In this case, trial treatment will be initiated 1 day after randomization which will be performed on Day -1. Once an eligible subject has signed the informed consent form (ICF), the center will use an IWRS and receive instructions regarding treatment assignment. Allocation to the 2 treatment arms will be in a ratio of 2:1.

Randomization will be stratified according to ECOG (0 versus 1) and the primary tumor site (oral cavity versus hypopharynx versus others) to balance these factors across the treatment arms and thus improve comparability of the results.

The randomization list will be generated by the designated contract research organization under the responsibility of the Sponsor's trial statistician. Specific details will be provided in a separate Manual of Operations.

6.4 Noninvestigational Medicinal Products to be Used

6.4.1 Chemotherapy

All subjects will receive chemotherapy for up to 6 cycles. As a rule, each cycle will last 21 days. In the absence of PD and unacceptable toxicity, subjects will receive 6 cycles of chemotherapy. The start of each cycle of chemotherapy will be defined by the start of cisplatin infusion (or carboplatin infusion, if cisplatin have been switched to carboplatin). Chemotherapy should be administered, if possible, on the same day of each cycle with no more than 3 days deviation.

Details of chemotherapy regimens are given in Table 6.4.

Table 6.4 Chemotherapy Regimen Every 21 Days in Arm A and B

Order of administration	Drug	Dose
First	Cisplatin infusion (refer to China package insert) on Day 1	75 mg/m ²
In the case of cisplatin intolerability ¹	Carboplatin infusion time of 15 minutes or longer, and in accordance with the China package insert on Day 1	AUC 5
Then	5-Fluorouracil Day 1 to Day 5	750 mg/m²/day continuous infusion

Abbreviation: AUC, area under serum concentration time curve.

6.4.1.1 Selection and Timing of Chemotherapy

6.4.1.1.1 Cisplatin

Cisplatin (75 mg/m²) will be administered as intravenous infusion (refer to China package insert) on Day 1 of each 21-day treatment cycle.

For any BSA value more than 2.0 m², the cisplatin dosage must be restricted to the dose appropriate for a BSA of 2.0 m². Adequate hydration and maintenance of sufficient urinary output is mandatory. Centers should follow their related local practice and the approved local package insert or the following hydration scheme:

- Before cisplatin: 2 liters of any fluid taken orally on the day before chemotherapy AND 1 liters orally plus a minimum of 500 mL of intravenous fluid given on the morning of cisplatin treatment. The 500 mL of intravenous fluid may be part of the antiemesis infusion.
- After cisplatin: Immediately after cisplatin, an intravenous infusion of 200 to 250 mL/hour of 5% dextrose in half normal saline, 5% dextrose in normal saline, or normal saline and 30 mEq KCl/L will be given for 4 to 6 hours.

Total hydration fluid volume, including enteral and parenteral, should be at least 3500 mL on the day of cisplatin administration.

There must be at least 1 hour between the end of the cetuximab infusion and the start of the cisplatin infusion. Intravenous prehydration can be performed concomitant to cetuximab administration but a separate line must be used.

Document No. CCI
Object No.

¹ If cisplatin results in a nonhematologic toxicity (see Section 6.4.1.2.2), cisplatin may be replaced by carboplatin in subsequent cycles.

Antiemetic prophylaxis is mandatory to prevent acute and delayed nausea and vomiting due to the high emetogenicity of cisplatin. It is highly recommended that the guidelines of the Multinational Association of Supportive Care in Cancer and the American Society of Clinical Oncology are followed, i.e., inclusion of dexamethasone, a 5-hydroxytryptamine-3 antagonist and a neurokinin-1 antagonist.

All infusions and medications given for hydration, urinary output maintenance and antiemesis must be documented in the eCRF. Investigators should refer to the approved cisplatin package insert for additional information such as safety issues, adverse reactions, and storage information.

Exact documentation of the actual doses, dates, and start and end times of infusions is mandatory.

6.4.1.1.2 Carboplatin

If cisplatin results in a nonhematologic toxicity (see Section 6.4.1.2.2), carboplatin at a dose of target AUC=5 may be used as the replacement of cisplatin in subsequent cycles. The decision needs to be made in discussion with the Medical Monitor on a case-by-case basis.

Carboplatin will be administered using an intravenous infusion of 15 minutes or longer (refer to China package insert) on Day 1 of each 21-day treatment cycle. The dose of carboplatin will be calculated considering the subject's renal function as described by the glomerular filtration rate using the Calvert formula or the Chatelut formula, given that the target AUC is 5.

For those subjects in Arm A, there must be at least 1 hour between the end of the cetuximab infusion and the start of the carboplatin infusion.

Exact documentation of the actual doses, dates, and start and end times of infusions is mandatory.

6.4.1.1.3 5-Fluorouracil

Investigators should treat subjects with commercially available forms of 5-FU, and must refer to the approved 5-FU prescribing information on dosage and administration, safety issues (warnings, precautions), adverse reactions, dose reductions and omissions. Investigators should also follow their related local practice for the administration of 5-FU.

5-Fluorouracil will be administered as a dose of 750 mg/m²/day as a continuous intravenous infusion over 24 hours a day from Day 1 to Day 5 (± 6 hours of the overall duration) of each 21-day treatment cycle. Administration of 5-FU is to start upon completion of cisplatin/carboplatin administration and may be performed via the same infusion line.

For those subjects in Arm A, there must be at least 1 hour between the end of the cetuximab infusion and the start of the 5-FU infusion.

Exact documentation of the actual doses, dates, and start and end times of infusions is mandatory.

6.4.1.1.4 Criteria for Starting the Next Cycle of Chemotherapy

Before starting the next cycle of chemotherapy, the following criteria must be fulfilled:

- Absolute neutrophil count (ANC) is $\ge 1.5 \times 10^9 / L$.
- Platelet count is $\geq 100 \times 10^9 / L$.
- Nonhematologic chemotherapy-related toxicities have resolved to ≤ Grade 1 or baseline (excluding weight loss, skin reactions, paronychia, fatigue, ototoxicity or neurotoxicity which must have resolved to ≤ Grade 2).

If these criteria are not met, the start of the next cycle must be delayed to allow for recovery. If a delay of more than 21 days is necessary as a result of an unresolved toxicity, one or both of the chemotherapeutic drugs should be discontinued.

If the start of the next cycle must be delayed due to either a cisplatin/carboplatin-, or 5-FU-related toxicity, the start of the other compound should also be postponed. However, if either cisplatin/carboplatin or 5-FU dosing must be permanently discontinued, dosing should be continued with the remaining compound according to the schedule.

The BSA must be recalculated and the cisplatin and 5-FU doses adapted accordingly before each subsequent cycle (for formula see Section 6.4.1.1.1). A delay in the next cycle of up to 3 calendar days from the calculated Day 1 of that cycle for administrative reasons such as a weekend is at the discretion of the treating Investigator.

For those in Arm A, in case of cetuximab-related toxicity, chemotherapy will not be delayed and the planned schedule for administration should be maintained. If cetuximab treatment is terminated for a cetuximab-related toxicity, chemotherapy will be continued. If chemotherapy is completely terminated for a related toxicity, cetuximab may be continued as monotherapy until either PD, as assessed by the Investigator, an unacceptable toxicity or withdrawal of consent.

6.4.1.2 Dose Reductions of Chemotherapy

Every effort will be made to administer the full doses of cisplatin/carboplatin and 5-FU.

Dose reductions are always based on the dose of the previous cycle. Only 2 dose reductions for cisplatin and 5-FU and 1 dose reduction for carboplatin are permitted. If further toxicity occurs or the criteria for resuming treatment are not met, the subject must be withdrawn from chemotherapy (see Table 6.5).

Table 6.5 Dose Reductions for Chemotherapy

	Dose reduction levels	Dosage ¹
Cisplatin	0	75mg/m ²
	-1 (decreased by 20%)	60mg/m ²
	-2 (decreased by 20% from -1 level)	48mg/m ²
Carboplatin ² -	0	AUC 5
	-1 (decreased by 20%)	AUC 4
5-Fluorouracil	0	750mg/m ²
	-1 (decreased by 20%)	600mg/m ²
	-2 (decreased by 20% from -1 level)	480mg/m ²

Abbreviation: AUC, area under serum concentration time curve.

- 1 The doses which have been reduced for toxicity must not be re-escalated.
- 2 Carboplatin can be considered, if the subject experiences a nonhematologic toxicity. The starting dose of carboplatin would be the first dose level of AUC 5 at the Investigator's discretion.

Dose adjustments are to be made according to the body system showing the greatest degree of toxicity experienced during the previous cycle. Toxicities will be graded using the CTCAE version 4.03.

All implemented dose reductions are permanent. The doses must be modified according to the lowest hematology values and the highest degree of nonhematologic toxicities observed at the scheduled date of chemotherapy. If a subject develops several different toxic effects and there are conflicting recommendations, the dose modification will be based on the AE on the scheduled day of treatment.

Dose reduction and delays and related management will be documented in the subject's medical record and in the related section in the eCRF.

If a subject has a Grade 3 or 4 toxicity after 2 dose reductions, or if a treatment delay is longer than 3 consecutive weeks, then the discontinuation of chemotherapy treatment has to be considered.

For those in Arm A, chemotherapy will not be delayed for cetuximab-related toxicities.

Major toxicities observed with cisplatin: nephrotoxicity; ototoxicity; myelodepression with leukopenia, thrombocytopenia and anemia; infectious complications; nausea and vomiting; and peripheral neuropathies.

Renal function will be assessed on a regular basis as specified in the protocol (see Table 1.1). Cisplatin should be used with caution in subjects with pre-existing peripheral neuropathy. Cisplatin is contraindicated in subjects with a pre-existing hearing deficit. Audiometric testing and periodic neurological examination at baseline and during treatment are recommended to monitor the effects of cisplatin on hearing and neurological function.

Major toxicities observed with carboplatin: myelodepression with thrombopenia, leucopenia, neutropenia and/or anemia; infectious complications; nausea and vomiting; ototoxicity; and peripheral neuropathies.

Major toxicities observed with 5-FU:

- Cardiac toxicity: The typical signs of cardiac toxicity related to 5-FU are ischemic pain occurring a few hours after a bolus or after the start of a continuous infusion, together with characteristic ECG changes. Silent ECG alterations may also occur. Myocardial infarction has been reported. Thus, treatment with 5-FU must be stopped in subjects who develop such symptoms or have any other cardiac events of unclear origin during or after treatment with 5-FU.
- Hand-Foot syndrome: Subjects treated with 5-FU may develop hand-foot syndrome, characterized by redness and swelling of the palms and soles of the feet. Mild hand-foot syndrome is painless, but in 10 to 15% of cases it can be painful and is usually associated with blisters, ulcerations, cracks, and desquamation. Pyridoxine (vitamin B6) at 100-150 mg per day may be helpful.
- Diarrhea and mucositis: Subjects treated with 5-FU may develop mucositis, or more commonly diarrhea. In case of diarrhea, symptomatic treatment with loperamide is recommended.

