Subjects in both arms will receive a maximum of 6 cycles of chemotherapy of 75 mg/m^2 cisplatin as intravenous infusion (refer to China package insert) on Day 1 of each 21-day treatment cycle, and then 750 mg/m^2 /day of 5-FU as a continuous intravenous infusion over 24 hours \pm 6 hours a day from Day 1 to Day 5 of each 21-day treatment cycle.

In the case of cisplatin-related nonhematologic toxicity, cisplatin may be replaced by carboplatin at a dose of target area under the serum concentration time curve of 5 in subsequent cycles. The decision needs to be made in discussion with the Medical Monitor on a case-by-case basis. Carboplatin will be administered using an intravenous infusion of 15 minutes or longer, and in accordance with the China package insert on Day 1 of each 21-day treatment cycle.

Planned treatment duration per subject:

The treatment duration per subject may vary. Subjects will be treated with a maximum of 6 cycles of chemotherapy and/or cetuximab weekly in the absence of PD, as assessed by the Investigator, and unacceptable toxicity. Subjects (in Arm A) who demonstrate at least a tumor response of stable disease (RECIST version 1.1) after 6 cycles of trial treatment will continue monotherapy with cetuximab until either PD or occurrence of unacceptable toxicity. Subjects who stop treatment before reaching PD will continue to have tumor assessments (CT or MRI) every 6 weeks until either PD, the start of a new antitumor treatment, death, or termination of the trial, or loss of follow up, whichever comes first. Upon occurrence of PD, all trial treatments should be discontinued.

Sample Size Calculation: CCI

Randomization: Randomization will be performed centrally using an interactive web response system (IWRS). A central stratified permuted block randomization procedure will be used to balance between treatment arms. The stratification factors are ECOG performance status (0 versus 1) and the primary tumor site (oral cavity versus hypopharynx versus others).

Statistical Analyses:

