5.3.2 Exclusion Criteria

Subjects are not eligible for this trial if they fulfill any of the following criteria:

- 1. Prior systemic chemotherapy, except if given as part of multimodal treatment for locally advanced SCCHN that was completed more than 6 months before randomization.
- 2. Major surgery or irradiation within 4 weeks before randomization.
- 3. Previous treatment with monoclonal antibody or signal transduction inhibitors targeting EGFR.
- 4. Nasopharyngeal carcinoma.
- 5. Known allergic reaction against any of the components of the trial treatment.
- 6. Active infection including active tuberculosis, known and declared human immunodeficiency virus (HIV) infection, or active hepatitis B/C virus (HBV/HCV) infection resulting in an impaired liver function or cirrhosis (see Section 7.2.4).
- 7. History of organ allograft, autologous/allogeneic stem cell transplantation, and renal replacement therapy.
- 8. Asymptomatic severe hypertension or hypertensive crisis defined as systolic blood pressure ≥180 mmHg and/or diastolic blood pressure ≥110 mmHg under resting conditions.
- 9. Impaired cardiac function, evidenced by any of the following conditions:
 - o Left ventricular ejection fraction < 45%
 - Serious arrhythmia
 - Unstable angina pectoris
 - o Congestive heart failure New York Heart Association class III or IV
 - o Myocardial infarction within the 12 months before randomization
 - o Pericardial effusion.
- 10. Known central nervous system metastasis and/or leptomeningeal disease. Subjects with neurological symptoms should undergo a CT/MRI of the brain to exclude brain metastasis.
- 11. Known uncontrolled diabetes mellitus, pulmonary fibrosis, interstitial lung diseases, acute pulmonary diseases, or liver failure.
- 12. Peripheral neuropathy or hearing loss ≥Grade 2.
- 13. Subjects not recovered from any acute effects of prior surgery, chemotherapy, or radiation therapy, that is, to \leq Grade 1 (CTCAE, version 4.03). Chronic late toxicities resulting from

prior radiation and/or surgery (pharyngeal/laryngeal toxicity, i.e., xerostomia, speech, swallowing abnormalities etc.) are permitted if nutritional status is stable.

- 14. Known alcohol and/or drug abuse.
- 15. Medical or psychological condition that would not permit the subject to complete the trial or sign informed consent.

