- 16. Past or current history of neoplasm other than SCCHN, except for curatively treated nonmelanoma skin cancer, in situ carcinoma of the cervix, or other cancer curatively treated and with no evidence of disease for at least 5 years.
- 17. Any investigational medication within 30 days before randomization.
- 18. Female subjects who are pregnant (absence to be confirmed by serum β-human chorionic gonadotropin [HCG] test) or breast feeding, or males and females of reproductive potential not willing or not able to employ a highly effective method of birth control/contraception to prevent pregnancy from 2 weeks before receiving trial treatment until 3 months after receiving the last dose of trial treatment. A highly effective method of contraception is defined as having a low failure rate (< 1% per year) when used consistently and correctly.
- 19. Concurrent treatment with a prohibited medication (see Section 6.5.2).
- 20. Subjects with any concurrent medical condition or disease that will potentially compromise the conduct of the trial at the discretion of the Investigator.
- 21. Legal incapacity or limited legal capacity.

Subjects must fulfill all eligibility criteria to be enrolled in this trial. No exemption from any inclusion and exclusion criteria will be allowed. If any deviation from eligibility is retrospectively detected for an already enrolled subject, the Investigator and Sponsor must decide immediately whether it is safe to treat this subject further within the trial (see Section 5.4.2).

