6.4.1.2.2 Nonhematologic Toxicities

If a subject has a Grade 3 or 4 toxicity, as defined in Table 6.8, after 2 dose reductions, or if a treatment delay is longer than 3 consecutive weeks, then the discontinuation of chemotherapy treatment has to be considered.

Table 6.8 Criteria for Dose Reductions Based on Nonhematologic Toxicities on the Scheduled Day of Treatment

Toxicity	Grade ¹	Action to be taken
Mucositis	Grade 1	Delay chemotherapy treatment until Grade 0
	> Grade 1	Delay chemotherapy treatment until Grade 0; dose reduction of all further doses of 5-FU only by 20%
Diarrhea	Grade 1	Delay chemotherapy treatment until Grade 0
	> Grade 1	Delay chemotherapy treatment until Grade 0; dose reduction of all further doses of 5-FU only by 20%
Hypercreatinemia	≥ Grade 1	Delay chemotherapy treatment until Grade 0, change cisplatin to carboplatin
Ototoxicity	Grade 2	Dose reduction of all further doses of cisplatin by 20%
	> Grade 2	Delay chemotherapy treatment until ≤ Grade 2, change cisplatin to carboplatin
	> Grade 3	Stop carboplatin
Hand-foot syndrome	Grade 2	Delay chemotherapy treatment until ≤ Grade 1
	> Grade 2	Delay chemotherapy treatment until ≤ Grade 1; dose reduction of all further doses of 5-FU by 20%
Other organ toxicity ²	Grade 2	Delay chemotherapy treatment until Grade 1
	> Grade 2	Delay chemotherapy treatment until Grade 1 ³ ; dose reduction of all further doses of platinum-based treatment and 5-FU by 20% (or dose reduction of carboplatin to AUC 4 if applicable)
Sensory neuropathy	Grade 2	Dose reduction for all further doses of cisplatin by 20%
	> Grade 2	Stop cisplatin, change cisplatin to carboplatin
	> Grade 3	Stop carboplatin

5-FU: 5-fluorouracil.

The results of hematology and blood biochemistry analyses must be available before the start of each cycle of chemotherapy.

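### Section 6.4.1.2 contraindicates cisplatin in a pre-existing hearing deficit with no grade limit, but exclusion criterion 12 stops only Grade 2 or worse, so Grade 1 subjects are eligible and start on cisplatin

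*Protocol*

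**What the plan says.** Four parts of the protocol bear on this point.

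- **Contraindication.** The paragraphs on cisplatin toxicity in Section 6.4.1.2 state: "Cisplatin is contraindicated in subjects with a pre-existing hearing deficit". No grade, test or definition of a deficit is given. The sentence before it, on a different condition, is milder: "Cisplatin should be used with caution in subjects with pre-existing peripheral neuropathy".
- **Eligibility.** Exclusion criterion 12 in Section 5.3.2 reads "Peripheral neuropathy or hearing loss ≥Grade 2". It applies one threshold to neuropathy and hearing alike. The same section closes by ruling out exemptions from the criteria.
- **Starting platinum.** The Synopsis says "Subjects in both arms will receive a maximum of 6 cycles of chemotherapy", with cisplatin given on Day 1 of each cycle. Table 6.4 and Section 6.4.1.1.1 repeat this.
- **Carboplatin.** Section 6.4.1.1.2 provides that, once cisplatin has produced a nonhematologic toxicity, carboplatin "may be used as the replacement of cisplatin in subsequent cycles", after case-by-case discussion with the Medical Monitor.

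The SAP adds nothing specific. In its Appendix 1, a breach of criterion 12 falls under the general line for other eligibility failures, and no entry covers starting cisplatin in a subject with a hearing deficit.

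**The concern.** Eligibility and treatment instructions should not disagree about who may receive the backbone drug. Here they use different thresholds, and the subjects in between have no alternative at the first dose. A site working from Section 5.3.2 would enrol a candidate with Grade 1 hearing loss and give cisplatin. A site that also applies Section 6.4.1.2 would see a contraindication and might turn the same candidate away.

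Two things are at stake. The first is safety: a subject could be dosed against a warning in the protocol that governs the treatment. The second is consistency: with approximately 30 centers, who is enrolled at this margin would depend on which section the investigator relies on, and the protocol gives no rule for deciding.

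**Working it through.** No formula applies and the plan has no figure to reproduce. The check sets the rules side by side and follows one candidate through them.

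**Step 1. Compare the two thresholds.**

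| Rule | Place | Whom it covers |
|---|---|---|
| Cisplatin contraindicated | Section 6.4.1.2 | a pre-existing hearing deficit, no grade stated |
| Candidate excluded | Section 5.3.2, criterion 12 | hearing loss of Grade 2 or more |
| Covered by the first as worded, not by the second | | Grade 1 hearing loss |

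The last row assumes that Grade 1 hearing loss counts as a hearing deficit. Nothing in the text limits the term to Grade 2 or more.

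**Step 2. Look for another criterion that closes the gap.** Criterion 13 asks for recovery from acute effects of earlier treatment to Grade 1 or better, so Grade 1 passes there too. Criterion 20 excludes "Subjects with any concurrent medical condition or disease that will potentially compromise the conduct of the trial at the discretion of the Investigator". It is framed around trial conduct, is discretionary, and does not mention hearing.

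**Step 3. Follow the candidate to the first dose.** Cisplatin is the Cycle 1 platinum in both arms. Carboplatin needs a prior toxicity from cisplatin and begins in a later cycle. Section 6.2.1 and Figure 5.1 name cisplatin or carboplatin without that condition, but neither permits carboplatin as the first platinum, and Section 6.4.1 with the footnote to Table 6.4 confines it to later cycles. The Grade 1 candidate therefore has no route in Cycle 1 other than cisplatin.

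**Step 4. Test whether the graded ototoxicity rules settle the matter.** Section 6.4.1.1.4 lets the next cycle begin with ototoxicity at Grade 2 or below. Table 6.8 lists no action at Grade 1. At Grade 2 its action is "Dose reduction of all further doses of cisplatin by 20" percent, and above Grade 2 it delays treatment and changes to carboplatin. These rules govern toxicity found once chemotherapy is under way. They do not say whether a subject who arrives with a deficit may start.

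**Step 5. Look for a statement of precedence.** None was found. No section says that criterion 12 defines the contraindication, or that Section 6.4.1.2 adds to the eligibility criteria.

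**Step 6. Compare with neuropathy.** Advice to use caution is compatible with excluding only Grade 2 or more. For hearing, Section 6.4.1.2 uses a stronger term while criterion 12 keeps the same threshold. The mismatch is specific to hearing.

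**The case against.** The best answer is that Section 5.3 alone governs enrolment and gives one clear threshold. On this view the sentence in Section 6.4.1.2 is background safety text inside a dose-reduction section, close in style to product labelling, and Section 6.4.1.1.1 sends investigators to the cisplatin package insert for safety matters. Criterion 12 would then be the working form of the warning. The graded rules in Section 6.4.1.1.4 and Table 6.8 point the same way, since none of them stops cisplatin at Grade 1, which leaves one ungraded sentence as the outlier.

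Part of this stands. The sentence is not an eligibility criterion, the term it uses is undefined, and the insert is not available to show what was meant. An investigator with doubts could also use criterion 20. None of it reconciles the two statements, though. The protocol does not say that criterion 12 defines the contraindication, the graded rules concern events on treatment, and individual discretion can produce the variation between sites described above.

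A reader might also fault the protocol because audiometry is only advised ("Audiometric testing and periodic neurological examination at baseline and during treatment are recommended") and has no row in Table 1.1. That is not a contradiction: a recommended test need not appear in a schedule of required assessments, and Section 7.4.4.2 already includes the ears and the neurological system in the physical examination.

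**Conclusion.** The two statements are inconsistent in the current text and should be reconciled. As written, a subject with Grade 1 hearing loss is not excluded by criterion 12, must start on cisplatin in either arm, and falls within the wording of a contraindication that carries no grade limit. The conclusion rests on one reading, that Grade 1 hearing loss is a hearing deficit. The documents neither confirm nor rule this out, and that silence is itself part of the fault.

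Three stronger readings are not supported.

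- A reader might infer that the protocol expressly bars cisplatin at every grade. It does not. It omits a grade, which leaves the matter open.
- A reader might estimate how many of the 240 subjects are affected. The documents give no rate of Grade 1 hearing loss, and a share of candidates could not simply be applied to the number randomized.
- A reader might infer bias in the trial's result. Both arms receive cisplatin under the same rules and criterion 12 applies before randomization. No effect is shown on the randomized comparison, the 144 progression-free survival events or the 240-subject target.

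The matter is subject safety and uniform enrolment, not the validity of the analysis.

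**What to change.** Reconcile exclusion criterion 12 with the hearing statement in Section 6.4.1.2, and check both against the platinum provisions in Sections 6.4.1 to 6.4.1.1.2. The eligibility criterion and the contraindication should use the same threshold and the same term for hearing loss, and the protocol should state how a candidate with Grade 1 hearing loss is handled. Which statement stands is for the clinical team.

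The cost is a clarification of a few lines. Depending on the decision, some candidates may be handled differently. Section 5.1 anticipated recruitment to the end of 2017, so if enrolment has closed, what remains is to correct the text and to list subjects with a baseline hearing deficit documented in the medical history who received cisplatin. No change to the sample size, the event target or the primary analysis is needed.
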